## 18.7 eGFR category

The definition of eGFR categories is presented in Table 1.

**Table 1 eGFR categories**

eGFR categories (mL/min/1.73 m  )
≥90
60 to 89
30 to 59
15 to 29
<15

Abbreviations: GFR, Glomerular filtration rate.

The eGFR will be calculated according to the MDRD (Modification of Diet in Renal Disease) formula:

$$\text{eGFR (mL/min/1.73 m}^2\text{)} = 175 \times (\text{S}_{\text{cr}})^{-1.154} \times (\text{Age})^{-0.203} \times (0.742 \text{ if female}) \times (1.212 \text{ if African American}).$$

Where  $\text{S}_{\text{cr}}$  is serum creatinine in  $\mu\text{mol/L}$ .

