7.3.2 Exclusion criteria

The presence of any of the following will exclude a patient from inclusion in the study:

1. Use of specified pain relief medications or biologics (including glucocorticoids, narcotics, paracetamol/acetaminophen, NSAIDs, colchicine, IL-blockers and tumor necrosis factor [TNF] inhibitors) within specified periods (see Appendix 1) prior to randomization.
2. Contraindication to triamcinolone.
3. Polyarticular gouty arthritis involving more than 4 joints.
4. Rheumatoid arthritis, evidence/suspicion of infectious/septic arthritis, or other acute inflammatory arthritis.
5. History of malignancy within the past 5 years. Exceptions are basal cell skin cancer, carcinoma-in-situ of the cervix or low-risk prostate cancer after curative therapy.
6. Known hypersensitivity to *Escherichia coli*-derived proteins, Kineret® (anakinra), Kenalog® (triamcinolone acetonide) or any components of the products.

7. Participation in another concurrent investigational study within 30 days of randomization or intake of an investigational drug within five times the half-life of that investigational drug has passed.
8. Previous inclusion in this study.
9. Known presence or suspicion of active or recurrent bacterial, fungal or viral infections, including tuberculosis, or HIV infection or hepatitis B or C infection.
10. Presence of severe renal function impairment chronic kidney disease (CKD) stages 4 and 5 (estimated creatinine clearance <30 mL/min/1.73m²).
11. Presence of neutropenia (ANC $< 1.5 \times 10^9$ /L).
12. Uncontrolled clinically significant hematologic, pulmonary, endocrine, metabolic, gastrointestinal, CNS or hepatic disease as judged by the investigator.
13. History of myocardial infarction, unstable angina, cerebrovascular events, or coronary artery bypass grafting, New York Heart Association (NYHA) class III or IV heart failure within the previous 3 months prior to Visit 1.
14. ECG with clinically relevant finding making the patient not appropriate for IMP treatment, as judged by the investigator.
15. Patients with a documented history of alcohol or substance abuse within 12 months prior to randomization (consumption of > 21 units of alcohol/week is considered alcohol abuse).
16. Patients who have undergone major surgery within 2 weeks prior to randomization, or have an unhealed operation wound/s.

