9.3.9 Exploratory subgroup analyses

In order to examine the consistency of the treatment effect, the primary analysis will be repeated within predefined subgroups using the ITT population. These subgroups will include the randomization strata, ULT usage (yes/no) and BMI (<30.0 and \geq 30.0 kg/m²), as well as age (<65 years and \geq 65 years), sex, race, renal function (CKD stage 1, 2 and 3) and usage of rescue medication during the first flare (yes/no). For each subgroup, the estimated change in pain intensity in each treatment group (anakinra and triamcinolone), the estimated difference in change in pain intensity between treatments and the corresponding 95% confidence intervals will be presented. P-values will not be presented. Further, the change in pain intensity will also be evaluated for the two anakinra doses for each subgroup.

Further subgroup analyses may be defined in the statistical analysis plan.

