### **11.3 Medical and surgical history and concurrent illnesses**

All medical and surgical history data will be coded using the MedDRA Version 19.1 and the same version will be used throughout the study.

Medical and surgical history at baseline will be presented by SOC and PT for the ITT, PP, and safety populations. Medical and surgical history reported after randomization will be presented separately (see Section 18.6).

Detailed information on the presence of the following selected comorbidities will be presented in a separate table for the ITT, PP, and safety populations: eGFR category, current or previous symptoms of heart failure, diabetes mellitus, hypertension, obesity, cardiovascular disease, hyperlipidemia, cerebrovascular disease and osteoporosis (see Sections **Error! Reference source not found.**, 18.8, 18.9, 18.10 and 18.11).

Data from physical examination will be presented as “normal” or “abnormal” at Day 1 and Day 15 for each flare for the ITT, PP, and safety populations. Any persisting abnormalities should be stated each time the examination is performed in medical history and new abnormalities should be recorded as AEs.

Baseline ECG will be presented for each flare.

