#### **14.1.1 Subgroup analyses**

In order to examine the consistency of the treatment effect, the MMRM model used for the primary analysis will also be used within the following subgroups, using the ITT population:

- ULT usage (yes/no).
- BMI ( $<30.0$  and  $\geq 30.0$  kg/m^2).
- Age ( $<65$  years and  $\geq 65$  years).
- Sex (male, female).
- Race (White and Other).
- Renal function (eGFR category  $\geq 90$ ,  $\geq 60 - <90$ ,  $\geq 30 - <60$ ).
- Usage of rescue medication up to 72 hours during for the first flare (yes/no).

For each subgroup, the estimated change in pain intensity in each treatment group (anakinra and triamcinolone), the estimated difference in change in pain intensity between treatments and the corresponding 95 % confidence intervals will be obtained from the model. P-values will not be presented. Further, the change in pain intensity will also be evaluated for the 2 anakinra doses for each subgroup.

The estimated difference in change in pain intensity between anakinra and triamcinolone and the corresponding 95 % confidence intervals will also be presented graphically in a forest plot.

To avoid too small subgroups in the analysis regarding race, American Indian or Alaska Native, Asian, Black or African American, Native Hawaiian or Other Pacific Islander will be grouped together with Other.

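### The SAP's eGFR formula takes creatinine in µmol/L with a constant that works only in mg/dL, so every plausible patient falls below 15 and the renal subgroups are empty

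*SAP*

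**What the plan says.** SAP 18.7, under Table 1, says "The eGFR will be calculated according to the MDRD (Modification of Diet in Renal Disease) formula". The equation is 175 × Scr^-1.154 × Age^-0.203, multiplied by 0.742 for women and by 1.212 for African American patients. The next line says that Scr "is serum creatinine in" µmol/L. No conversion step and no other eGFR formula appears in the SAP or the protocol.

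Table 1 sets the classes ≥90, 60 to 89, 30 to 59, 15 to 29 and <15 mL/min/1.73 m². They are used in two places:

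- SAP 14.1.1 lists "Renal function (eGFR category" ≥90, ≥60 to <90 and ≥30 to <60) among the subgroups of the primary endpoint, with a forest plot. The matching protocol entry in 9.3.9 is "renal function (CKD stage 1, 2 and 3").
- SAP 11.3 includes eGFR category in the comorbidity table for the ITT, PP and safety populations: "Detailed information on the presence of the following selected comorbidities will be presented in a separate table".

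Protocol 7.3.2, exclusion 10, reads "Presence of severe renal function impairment chronic kidney disease (CKD) stages 4 and 5", defined there as an estimated creatinine clearance below 30 mL/min/1.73 m².

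**The concern.** The stated constant and the stated unit do not fit together. Creatinine enters with a negative power, so a number 88.4 times larger shrinks the result by a factor of 88.4^1.154. The plan expects enrolled patients to spread over the three classes from 30 upwards, but its own derivation puts them near zero.

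Run as written, a predefined subgroup analysis of the primary endpoint has no patients in any stratum, and a baseline table describes the whole trial population as having an eGFR below 15. Renal function is not an incidental covariate here: protocol 5.3 says that anakinra elimination depends on it and that exposure was correlated with the degree of renal impairment.

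**Working it through.** **Inputs from the documents.** Constant 175, exponents -1.154 and -0.203, factors 0.742 and 1.212, and the unit µmol/L (SAP 18.7); classes (SAP Table 1); subgroups (SAP 14.1.1); exclusion below 30 (protocol 7.3.2); age 18 or over (protocol 7.3.1).

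**Assumptions.** The documents do not give the unit conversion (1 mg/dL = 88.4 µmol/L) or a creatinine range. I take 40 to 300 µmol/L and ages up to 95, and also look below 40. The documents state no eGFR value, so there is no figure to reproduce.

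**Step 1: one patient, both units.** Man aged 55, no race factor, creatinine 88.4 µmol/L = 1.0 mg/dL.

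- As written: 175 × 88.4^-1.154 × 55^-0.203 = 0.44
- In mg/dL: 175 × 1.0^-1.154 × 55^-0.203 = 77.6
- Ratio: 88.4^1.154 = 176.3

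**Step 2: across creatinine values.** Man aged 50, no race factor.

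| Creatinine, µmol/L (mg/dL) | As written | With mg/dL |
|---|---|---|
| 70.7 (0.8) | 0.58 | 102.4 |
| 88.4 (1.0) | 0.45 | 79.1 |
| 133 (1.5) | 0.28 | 49.4 |
| 177 (2.0) | 0.20 | 35.5 |

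Entered in mg/dL, the same constant fills the three classes that the plan expects. Entered in µmol/L, it fills none of them.

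**Step 3: the full range.** Over 40 to 300 µmol/L, ages 18 to 95, both sexes, with and without the factor 1.212, the formula as written gives 0.07 to 1.67. If the lower limit is 30 or 20 µmol/L, the maximum rises to 2.33 or 3.72.

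**Step 4: invert the formula.** With k the product of the sex and race factors, the creatinine that gives eGFR = g is Scr = (175 × Age^-0.203 × k / g)^(1/1.154). The most favourable case is a man aged 18 with the factor 1.212:

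- g = 2 needs at most about 34 µmol/L
- g = 15 needs at most 6.0 µmol/L
- g = 30 needs at most 3.3 µmol/L (about 0.04 mg/dL)

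The class result therefore does not depend on the assumed range: leaving the <15 class would take a creatinine of about 6 µmol/L or less.

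**Step 5: equivalent constant in µmol/L.** 175 × 88.4^1.154 = 175 × 176.28 ≈ 30,849.

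**The case against.** The best case against giving this weight is that its reach is small and the error would show itself. Protocol 9.3.9 calls the subgroup analyses exploratory, and both documents say that no p-values will be given for them. The primary model has no renal term. Sample size, analysis populations, the other subgroups and the secondary endpoints do not use eGFR. An output with everyone in <15 cannot be mistaken for a real result, the method is named, and creatinine is collected, so the classes can be derived again without loss of data. All of this stands, and it limits the consequence to one subgroup factor and one baseline row.

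It does not remove the need to correct the SAP. SAP 6.1 has the SAP signed before the first database lock and unblinding, and then treats efficacy analyses of data up to Day 15 as final. A programmer who notices the problem after that point has to change a predefined derivation with treatment codes known.

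Two narrower points also stand. Eligibility is judged on local laboratory values, taken up to 72 hours before randomization (protocol 7.5.6.2), as an estimated creatinine clearance, and the SAP formula plays no part in it. A correct MDRD value could therefore put an eligible patient slightly under 30, and the exclusion criterion is only a coarse check on the derived classes. Protocol 5.3 also reports no relevant safety differences across degrees of renal impairment, which tempers the importance of the subgroup but not the error.

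**Conclusion.** The concern holds. The derivation in SAP 18.7 is wrong as written: results are about 176 times smaller than the same constant gives with mg/dL, and every plausible patient is classed as <15. All three renal subgroups in SAP 14.1.1 and their forest-plot rows would be empty, and the eGFR row of the comorbidity table would be false in all three populations.

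The only outside input is the fixed conversion 88.4. The creatinine range is an assumption that affects only the exact values: all results are below 2 for creatinine above about 34 µmol/L, and slightly higher values are possible below that, still far under 15. The evidence that mg/dL is the matching unit is internal: it yields values in the classes that the plan itself expects. The primary result, the sample size and eligibility are untouched. It is a must-fix because a prespecified analysis cannot be produced from the rule given, not because the trial's conclusion is at risk.

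**What to change.** In SAP 18.7, do one of the following before the first database lock:

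- define Scr in mg/dL and state that values in µmol/L are divided by 88.4; or
- keep µmol/L and replace 175 by about 30,849.

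The documents do not say in which unit creatinine will be delivered, so the text should also name the unit in the dataset and whether the central or the local value is used. Compare the derived classes with exclusion 10 as a gross check: a few values just under 30 can be legitimate, but a population below 15 cannot.

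A secondary edit in the same place: write the Table 1 classes as ≥60 to <90 and ≥30 to <60, and likewise ≥15 to <30. eGFR is continuous, so a value such as 89.5 has no class in the table at present, although SAP 14.1.1 has gap-free limits for its three subgroups.

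The main correction costs one line in the SAP and one in the derivation program. It needs no new data and no change to the protocol.

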## 18.8 Obesity

Obesity is defined as a BMI  $\geq 30$ .

## 18.9 Cardiovascular disease

Cardiovascular disease is defined as a history of angina pectoris or myocardial infarction.

## 18.10 Hyperlipidemia

Hyperlipidemia is defined as Cholesterol  $>240$  mg/dL or taking stable cholesterol-lowering treatments defined as ATC codes: C10, increased low-density lipoprotein levels ( $>160$  mg/dL), hypertriglyceridaemia (triglycerides  $>150$  mg/dL), or decreased high-density lipoprotein levels ( $<40$  mg/dL in male or  $<50$  mg/dL in female).

### **18.11 Cerebrovascular disease**

Cerebrovascular disease is defined as previous ischemic or hemorrhagic stroke, previous TIA, carotid or vertebral stenosis/occlusion.

### **18.12 Start of prior and concomitant medication**

If the start or end date of medication is (partly) missing so that categorization in time periods of medication cannot be done, the question regarding if medication was taken prior to the study will be used for the categorization.

### **18.13 Glucocorticoid use**

Glucocorticoid use is defined as ATC codes: H02A, H02B or M01BA.

### **18.14 ULT use**

ULT use during the study is defined as ATC codes: M04AA, M04AB or M04AX.

### **18.15 Study drug compliance**

The first IMP injections will be given at site (one i.m. and 2 s.c. injections) at Visit 1 and drugs for 2 days (24 and 48 hours) will be dispensed. At Visit 2 (72 hours) the 2 s.c. injections will be given at site and drug will be dispensed for one additional day (Day 5). The number of syringes given at site, the number of days for which IMP was dispensed (2 syringes per day) and number of syringes returned will be recorded in the CRF. The number of syringes used at home will be recorded in the eDiary at 24 and 48 hours and at Day 5.

Drug compliance will be calculated as:

$$\frac{([\text{Number of syringes dispensed} - \text{number of syringes returned}] / \text{number of syringes dispensed}) * 100}{}$$

Number of syringes dispensed will be calculated as:

$$\text{Total number of syringes supposed to be given at site at Visit 1 (3 syringes) and Visit 2 (2 syringes) + total number of syringes dispensed at Visit 1 and Visit 2}$$

Number of syringes returned will be calculated as:

$$\text{Number of unused syringes at site at Visit 1 and Visit 2 + total number of unused syringes returned}$$

## 18.16 Time windows for pain intensity assessments (Visual analogue scale – VAS- and Likert)

The time windows presented in Table 2 are used for collecting pain assessments in the eDiary at the nominal times for baseline, 6, 12, 18, 24, 36, 48, 72 hours and Days 5, 6, 7,8, 9, 10, 11, 12, 13, 14 and 15. Time for first IMP injection is time=0. For assessments where the nominal time would fall during the patients sleep, pain intensity was collected prior to sleep and at awakening. These assessments will be assigned to the nominal time if they fall within its below time-window.

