7.5.5 Efficacy assessments

7.5.5.1 Patient-assessed pain intensity, VAS scale

The patients will score their current pain intensity in the joint most affected (i.e., the index joint) on a continuous 0-100 mm visual analogue scale (VAS), ranging from no pain (0) to unbearable pain (100).

For each flare, the pain intensity will be assessed in the index joint and recorded in the patient diary prior to the first IMP administration. Subsequent pain assessment will be recorded in the patient diary at 6, 12, 18, 24, 36, 48, 72 hours and Day 5, 6, 7, 8, 9, 10, 11, 12, 13, 14 and 15. At 24, 48, 72 hours and Day 5, the assessments will take place just before IMP administration. If the time point for assessment occurs during sleep, pain intensity will be recorded just before and after sleep, and the assessment closest to the scheduled timepoint will be used in the analysis.

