## **3.3 Study endpoints**

### **3.3.1 Primary efficacy endpoint and secondary endpoints supporting the primary objective**

#### **3.3.1.1 Primary efficacy endpoint**

The primary efficacy endpoint is:

- The change in patient-assessed pain intensity from baseline to 24 to 72 hours (average of the assessments performed at 24, 48, and 72 hours) for the first flare.

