## 14 Efficacy analyses

### 14.1 Primary efficacy endpoint

The primary efficacy endpoint will be analyzed using the ITT population (primary population for evaluation) and will be based on observed data i.e. no missing data imputation for the primary analysis.

The primary endpoint is the change in patient-assessed pain intensity from baseline to 24 to 72 hours (average of the assessments performed at 24, 48 and 72 hours) for the patients' first flare (see Section 18.16 for time windows for pain intensity assessments).

Patients will score their pain intensity in the joint most affected at baseline (i.e., the index joint) on a 0 to 100 VAS, ranging from no pain (0) to unbearable pain (100) (see Section 18.17).

The comparison of primary interest is between anakinra (100 mg and 200 mg combined) and triamcinolone, and the null and alternative hypotheses with regard to this are defined as:

$$H_0: \mu_{\text{anakinra}} = \mu_{\text{triamcinolone}}$$

$$H_A: \mu_{\text{anakinra}} \neq \mu_{\text{triamcinolone}}$$

The primary endpoint will be estimated using a MMRM analysis with the measurements on the individual time points as responses (baseline, 6, 12, 18, 24, 48 and 72 hours), and with treatment (anakinra 100 mg, anakinra 200 mg and triamcinolone), ULT use (yes/no), BMI (<30.0 and  $\geq 30.0$  kg/m^2), visit and treatment-visit-interaction as fixed effects and center as random effect. The model is expressed as:

$$y_{ij} = \text{time}_j + \text{treat}_k + \text{time} \times \text{treat}_{jk} + \text{ULT}_l + \text{BMI}_m + \text{center}_n + \varepsilon_{ij}$$

where

$y_{ij}$  is the response for patient  $i$  on visit  $j$

$\text{time}_j$  is the visit effect (baseline, 6, 12, 18, 24, 48 and 72 hours),  $j=1, \dots, 7$

$\text{treat}_k$  is the treatment effect,  $k=1, 2, 3$

$\text{ULT}_l$  is the ULT strata effect (yes, no),  $l=1, 2$

$\text{BMI}_m$  is the BMI strata effect (<30.0,  $\geq 30.0$ ),  $m=1, 2$

$\text{center}_n \sim N(0, \sigma_c^2)$  and  $\varepsilon_{ij} \sim N(0, \sigma^2)$

The analysis will be based on a restricted maximum likelihood (REML) approach. The following order of covariance matrices will be used until convergence is met:

- i. Unstructured
- ii. Heterogeneous Toeplitz
- iii. Heterogeneous first order autoregressive
- iv. Homogeneous Toeplitz
- v. Homogeneous first order autoregressive

- vi. Heterogeneous compound symmetry
- vii. Homogeneous compound symmetry

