**Table 2 Time windows for pain intensity assessments (VAS and Likert)**

Nominal time	Time window	
	Start time (h)	End time (h)
Baseline		≤0
6 h	>0	≤9
12 h	>9	≤15
18 h	>15	≤21
24 h	>21	≤30
36 h	>30	≤42
48 h	>42	≤60
72 h	>60	≤84
Day 5	>84	≤108
Each following day until Day 15 but day 15 does not have an end.	+24	+24

Abbreviations: h, hours; VAS, Visual analogue scale.

If IMP is not taken the following rules will be used:

- For the first flare, for patients not receiving treatment the baseline VAS pain measurement from their date of randomization will be used as the baseline assessment.
- For subsequent flares, if a patient doesn't receive treatment, the flare will not be accounted for.

If multiple assessments fall within the same windows the following rules will be used:

- If multiple assessments fall into the same time window, the one closest to the nominal time will be used.
- If multiple assessments in the same time window are equidistant to the nominal time, the latest will be used.
- If multiple assessments have the exact timestamp, an average will be used.

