### **18.17 Pain intensity on Visual analogue scale (VAS)**

The patients will score their current pain intensity in the joint most affected (i.e., the index joint) on a continuous 0 to 100 VAS, ranging from no pain (0) to unbearable pain (100). The original 100 mm scale has been transferred into ePRO format and proportionally scaled down to 5 cm in length. The conceptual equivalency of the pen-and-paper and the ePRO format has been tested and is described in a Cognitive Debriefing and Usability Testing of Pain Scales for Gouty Arthritis Report.

For each flare, the pain intensity will be assessed in the index joint and recorded in the patient diary prior to the first IMP administration. Subsequent pain assessment will be recorded in the patient diary at 6, 12, 18, 24, 36, 48, and 72 hours and Days 5, 6, 7, 8, 9, 10, 11, 12, 13, 14 and 15. At 24, 48, and 72 hours and Day 5, the assessments will take place just before IMP administration. If the time point for a specific assessment occurs during sleep, pain intensity will be recorded just before and after sleep, and the assessment closest to the scheduled time point will be used in the analysis (see Section 18.16).

For each time point (6, 12, 18, 24, 36, 48, and 72 hours and Days 5, 6, 7 and 8), the change from baseline in pain intensity on VAS is defined as:

$$\text{VAS pain intensity at specific time point} - \text{VAS pain intensity at baseline}$$

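### SAP 18.16 accepts before- and after-sleep pain readings only inside the Table 2 windows, contrary to protocol 7.5.5.1 and SAP 18.17/18.18, so 12 h and 18 h values can be missing although both readings were recorded

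*SAP*

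**What the plan says.** Protocol 7.5.5.1 covers VAS assessments whose scheduled time falls during sleep. Pain is recorded just before and just after sleep, and "the assessment closest to the scheduled timepoint will be used in the analysis". No window is attached. SAP 18.17 repeats the rule for VAS ("the assessment closest to the scheduled time point will be used in the analysis") and adds a cross-reference to 18.16. SAP 18.18 gives the same rule for Likert without a cross-reference. Protocol 7.5.5.2, on Likert, asks for both readings but does not say which one is analysed.

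SAP 18.16 covers both scales. It confirms that "pain intensity was collected prior to sleep and at awakening", and then restricts their use: "These assessments will be assigned to the nominal time if they fall within its below time-window". The tie-breaking rules under Table 2 work only within a window: "If multiple assessments fall into the same time window, the one closest to the nominal time will be used".

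The Table 2 windows that matter here, in hours after the first injection, are:

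| Nominal time | Window | Width |
|---|---|---|
| 6 h | >0 to ≤9 | 9 h |
| 12 h | >9 to ≤15 | 6 h |
| 18 h | >15 to ≤21 | 6 h |
| 24 h | >21 to ≤30 | 9 h |
| 36 h | >30 to ≤42 | 12 h |
| 48 h | >42 to ≤60 | 18 h |
| 72 h | >60 to ≤84 | 24 h |

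SAP Section 5, on changes from the protocol, mentions only anti-drug antibody analyses.

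**The concern.** A programmer cannot follow both rules. If 18.16 governs, a patient who slept through the 12 h or 18 h point and recorded pain on both sides, as the protocol asks, may still have a missing value there. The two readings were collected to cover exactly this situation.

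Change in VAS and Likert pain at 12 h and 18 h are named secondary endpoints supporting the primary objective (SAP 3.3.1.2). Each is reported with an estimate, confidence interval and p-value (SAP 14.2.1 and 14.2.2). The VAS values at these times are also responses in the primary mixed model (SAP 14.1). Avoidable gaps would appear as intermittent missingness in the pattern table (SAP 14.1.2.2.1). If the tipping point analysis is run, they would be imputed under missing at random although real readings exist.

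**Working it through.** **Figure in the plan.** The documents state no figure for readings lost to sleep, so there is none to reproduce. They also give no clock times for dosing or sleep. Those inputs are assumptions; the windows come from Table 2.

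**Condition for a loss.** Let D be the clock time of the first dose, B bedtime and S hours of sleep. The readings fall at B − D and B + S − D hours after dose. A window (a, b] is empty of both when B − D ≤ a and B + S − D > b, that is

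B − a ≤ D < B + S − b.

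This range of dose times has length S − (b − a). For the 12 h and 18 h windows that is S − 6 hours, so any sleep longer than 6 h creates some loss.

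**Worked case: sleep 23:00-07:00 (B = 23, S = 8), dose uniform over 08:00-18:00.**

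- 12 h: 23 − 9 = 14 to 31 − 15 = 16. Doses at 14:00-16:00 lose the value: 2/10 = 20%.
- 18 h: 23 − 15 = 8 to 31 − 21 = 10. Doses at 08:00-10:00 lose the value: 2/10 = 20%.
- The dose ranges do not overlap, so these are different patients.

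**Two single patients, same sleep.**

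- Dose 08:30: readings at 14.5 h and 22.5 h. Neither is in the 18 h window. The closest-reading rule would use 14.5 h, which is 3.5 h from nominal.
- Dose 14:30: readings at 8.5 h and 16.5 h. Neither is in the 12 h window. The closest-reading rule would use 8.5 h, also 3.5 h from nominal.

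The displaced readings fall in neighbouring windows, where a scheduled reading is normally closer to nominal.

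**Other schedules, dose uniform over 08:00-18:00.**

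| Sleep | 12 h lost | 18 h lost |
|---|---|---|
| 23:00-05:00 (6 h) | 0% | 0% |
| 23:00-06:00 (7 h) | 10% | 10% |
| 22:00-06:00 (8 h) | 20% | 10% |
| 23:00-07:00 (8 h) | 20% | 20% |
| 23:00-08:00 (9 h) | 30% | 30% |

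**Wider range**, with bedtimes 22:00-24:00 and several dosing spans between 07:00 and 20:00:

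| Sleep length | 12 h lost | 18 h lost |
|---|---|---|
| 6 h | 0% | 0% |
| 7 h | 8-13% | 0-13% |
| 8 h | 13-25% | 0-25% |
| 9 h | 25-38% | 0-38% |

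The upper end is a 9 h night with an 8 h dosing span: (9 − 6)/8 = 37.5%.

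**Other time points.** No 6, 24, 36, 48 or 72 h value was lost in any of these scenarios. The 24 h window is 9 h wide, so only a sleep longer than 9 h lying across all of it could empty it.

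**Precision.** A 20% loss raises the raw standard error at that time point by 1/√0.8 = 1.118, about 12%. The mixed model recovers part of this from neighbouring times, so 12% is a ceiling for that loss.

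**Closest-reading rule.** No 12 h or 18 h value is lost when both sleep readings exist. With 8 h sleep, the values that 18.16 would drop are filled by readings 3 to 4 h from nominal. Table 2 already accepts readings up to 6 h away at 6 h (just after 0 h) and at 24 h (30 h).

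**The case against.** **The percentages rest on assumptions.** This stands. The heavy weight on early doses is also doubtful. Visit 1 requires consent, examination, ECG, eligibility review, randomization and blood sampling before the first injection (protocol 7.5.1.3). If dosing runs 10:00-18:00 with sleep 23:00-07:00, the 18 h loss is 0% and the 12 h loss is 2/8 = 25%. In-patients and emergency department patients are also treated. The 20% figures are therefore an illustration.

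**The primary endpoint might seem damaged.** A reader might infer this because the 12 h and 18 h values are in the primary model. The documents do not support it. The endpoint is the "average of the assessments performed at 24, 48, and 72 hours", and none of those values was lost in any scenario. The 12 h and 18 h values are only additional responses, so the 24-72 h contrast should move little (reasoned, not simulated).

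**The readings might seem to be thrown away.** They are not. They stay in the dataset and can be used in an adjacent window. Time to onset, response and resolution use every measurement at its actual time (SAP 18.19 to 18.21), so those endpoints lose nothing.

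**The protocol might seem to be contradicted for both scales.** It is contradicted for VAS only. Protocol 7.5.5.2 has no closest-reading rule, so for Likert the conflict is within the SAP, between 18.16 and 18.18.

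**SAP 18.17 points to 18.16, which could be read as its operating limit.** This is a fair reading of 18.17. It leaves the conflict with protocol 7.5.5.1 and with 18.18, and Section 5 is silent.

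**Leaving the slot empty is defensible.** Labelling a 14.5 h reading as the 18 h value is imperfect, and a sponsor may prefer to rely on the model. That is a legitimate choice if it is stated consistently and declared.

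**Conclusion.** The two rules conflict. SAP 18.16 adds a window limit that protocol 7.5.5.1 (VAS) and SAP 18.17/18.18 (VAS and Likert) do not have, and Section 5 does not report it. Because the 12 h and 18 h windows are 6 h wide, a longer sleep can leave them empty although the patient recorded both readings.

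The size depends on dosing and sleep hours that the documents do not give. Under 23:00-07:00 sleep and uniform dosing over 08:00-18:00, about 20% of patients lose each value. Over the other assumptions tried, each loss runs from 0% to nearly 40%.

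The consequence is limited to precision and completeness of the 12 h and 18 h secondary comparisons. A reader might also infer bias between arms. The loss depends on dosing hour and sleep hours, and nothing in the documents shows that these differ by treatment.

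**What to change.** In SAP 18.16, state that when a nominal time falls during sleep, the closer of the before- and after-sleep readings is used for that time (the later if tied), even if it lies outside the Table 2 window. Apply Table 2 to all other readings. This agrees with protocol 7.5.5.1 and SAP 18.17/18.18.

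If the window limit is intended, amend 18.17 and 18.18 to say so and list it in Section 5 as a change from the protocol for VAS.

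The cost is SAP wording and one programming rule, settled before the first database lock. There are two reservations. With 8 h sleep, some 12 h and 18 h values would be up to about 4 h from nominal. The diary data must also show which readings were taken around sleep; the documents do not say whether they do, so this should be checked first.
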